- An IRR should be considered when onset is on the day of infusion (during or after the infusion) or the day after the infusion (irrespective of resolution date) for any infusion related reaction, drug hypersensitivity, anaphylactic reaction, hypersensitivity, and/or Type 1 hypersensitivity.

Signs and symptoms of IRRs and hypersensitivity/allergic reactions should be considered when onset is on the day of infusion (during or after the infusion) and resolved completely with the end date within 2 days after onset. Signs and symptoms may include but not limited to pruritus, rash, and hypoxemia.

Table 2 Treatment Modification of M7824 for Symptoms of Infusion-related Reactions Including Immediate Hypersensitivity

NCI-CTCAE Grade v5	Treatment Modification
Grade 1 – mild 
 Mild transient reaction; infusion interruption not indicated; intervention not indicated. 	
 Increased monitoring of vital signs as medically indicated as participants are deemed medically stable by attending Investigator.
Grade 2* – moderate 
 Therapy or infusion interruption indicated but if responds promptly to symptomatic treatment (for example, antihistamines, NSAIDs, narcotics, IV fluids); prophylactic medications indicated for \leq 24 hours. 	
 Stop infusion of the drug caused IRR. Increased monitoring of vital signs as medically indicated as participants are deemed medically stable by attending investigator. If symptoms resolve quickly or decreased to Grade 1, resume infusion at 50% of original rate with close monitoring of any worsening otherwise dosing held until resolution of symptoms with mandated premedication for the next schedule. If worsens to Grade 3 or 4, follow treatment modification guidelines accordingly.

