Grade 3 or Grade 4 – severe or life-threatening 
 Grade 3: Prolonged (e.g., not rapidly responsive to symptomatic medication and / or brief interruption of infusion); recurrence of symptoms following initial improvement; hospitalization indicated for clinical sequelae. Grade 4: Life-threatening consequences; urgent intervention indicated. 	
 Stop the infusion caused IRR immediately and disconnect infusion tubing from the participant with additional appropriate medical measures and close monitoring until deemed medically stable by attending Investigator. Hospitalization may be indicated. Restart the medication taking out the drug that is the cause of IRRs from the next scheduled visit

IV = intravenous, NCI-CTCAE = National Cancer Institute-Common Terminology Criteria for Adverse Event, and NSAIDs = nonsteroidal anti-inflammatory drugs.

Once the M7824 infusion is interrupted or rate reduced to 50% of previous infusion rate, it must remain decreased for all subsequent infusions. For Grade 3 or 4 IRRs, M7824 discontinuation is mandated.

For all types and grades of infusion reactions, details about drug physical constitution, method of preparation, and infusion must be recorded.

In the event of a Grade 2* IRR that does not improve or worsens after implementation of the dose modifications indicated in

Table (including reducing the infusion rate by 50%), the Investigator may consider treatment with corticosteroids and the infusion should be stopped for that day. At the next infusion, the Investigator may consider the addition of H2 blocker antihistamines (eg, famotidine or ranitidine), in addition to premedication, for select participants. However, prophylactic steroids are NOT permitted. At the next dose, if the participant has a second IRR Grade ≥ 2 on the slower infusion rate, with the addition of further medication to premedication, the infusion should be stopped and the participant removed from treatment.

Hypersensitivity Reaction

If a hypersensitivity reaction occurs, the participant must be treated according to the best available medical practice. A complete guideline for the emergency treatment of anaphylactic reactions according to the Working Group of the Resuscitation Council (United Kingdom) and can be found at <https://www.resus.org.uk/pages/reaction.pdf>. Participants should be instructed to report any delayed reactions to the Investigator immediately.

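### Section 6.2.3: an infusion reaction that does not respond to interruption, or returns on the slower rate, can fall under both mandated M7824 discontinuation and a rule that provides for re-infusion

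*Combined protocol and SAP*

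**What the plan says.** All the relevant text is in Section 6.2.3 of the combined protocol and SAP, in Table 2 and the text directly after it.

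- **Grade 2 definition (Table 2):** "Therapy or infusion interruption indicated but if responds promptly to symptomatic treatment".
- **Grade 2 action (Table 2):** the infusion is stopped. It resumes at half the original rate if symptoms resolve quickly or fall to Grade 1; "otherwise dosing held until resolution of symptoms with mandated premedication for the next schedule". The row ends: "If worsens to Grade 3 or 4, follow treatment modification guidelines accordingly".
- **Grade 3 definition (Table 2):** "Grade 3: Prolonged (e.g., not rapidly responsive to symptomatic medication and / or brief interruption of infusion); recurrence of symptoms following initial improvement". Hospitalization for clinical sequelae is a further criterion.
- **Grade 3 or 4 consequence (text after the table):** "For Grade 3 or 4 IRRs, M7824 discontinuation is mandated".
- **Grade 2\* paragraph (text after the table):** "In the event of a Grade 2* IRR that does not improve or worsens after implementation of the dose modifications indicated in" the table, where the modifications expressly include the 50% rate reduction, corticosteroids may be considered and the infusion is halted for the day. The paragraph continues: "At the next infusion, the Investigator may consider the addition of H2 blocker antihistamines". The participant leaves treatment if a second reaction of Grade 2 or higher occurs at that next dose, on the slower rate and with the extra premedication.

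Section 10.2 lists infusion-related reactions as adverse events of special interest (AESIs) and as an important identified risk of M7824.

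**The concern.** Table 2 uses response to interruption and treatment as the dividing line between Grade 2 and Grade 3. The Grade 2\* paragraph takes a reaction that has failed on that criterion, leaves it at Grade 2, and plans a further dose. An investigator with such a participant can find support in the same section for permanent discontinuation and for giving the next infusion. The first stake is participant safety, since the choice is between stopping the drug and re-exposing someone who has just reacted to it. The second is consistency of the safety tables: the same clinical course can be recorded as a Grade 2 or a Grade 3 AESI, depending on which provision the investigator read.

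**Working it through.** The protocol states no figure to reproduce on this point. The main check is a comparison of the provisions; the arithmetic only bounds the size.

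**Step 1. Courses that a Grade 2 reaction can take once the infusion is stopped.**

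- **A. Symptoms do not respond to stopping and treatment.** This fails the prompt-response criterion for Grade 2 and fits the Grade 3 example, "not rapidly responsive to symptomatic medication and / or brief interruption of infusion". If it is Grade 3, discontinuation is mandated. The Grade 2 row, however, holds dosing until symptoms resolve and then looks to the next scheduled dose with premedication. The Grade 2\* paragraph, if read to reach this case, also provides for a next infusion. **Two instructions.**
- **B. Symptoms improve, the infusion resumes at half rate, and symptoms return.** This fits the other Grade 3 criterion, recurrence after initial improvement, so discontinuation is mandated. The Grade 2\* paragraph, whose trigger includes the halved rate, keeps it at Grade 2 and provides for a next infusion. **Two instructions.**
- **C. Symptoms fall to Grade 1, the infusion resumes at half rate, and symptoms stay at Grade 1.** This is not clearly Grade 3. **No conflict shown.**
- **D. The reaction is judged to have worsened to Grade 3 or 4.** The escalation clause in the Grade 2 row sends the reader to the Grade 3 or 4 guidance. **No conflict if that clause is followed.**

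The conflict is therefore in courses A and B. The escalation clause does not remove it: it addresses worsening to Grade 3 or 4, not a failure to improve, and it does not say that recurrence on the slower rate is to be regraded.

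**Step 2. Upper bound on exposure.** Table 1 gives cycles 1 to 12 with visits on days 1 and 15; Section 6.2.2 gives M7824 on days 1 and 15 of each 28-day cycle.

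- Planned infusions: 12 × 2 = 24.
- Remaining after a reaction at dose 1: 24 − 1 = 23.

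This is a ceiling. It requires the reaction at the first dose, no second reaction of Grade 2 or higher at the next dose, and no later stop for progression, toxicity or withdrawal. If a second such reaction occurs at dose 2, the difference is that one infusion, stopped early.

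**Step 3. Effect of one regraded patient on a descriptive Grade 3 or higher rate.**

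- Lead-in, 8 patients (Section 13.2): 1/8 = 12.5 percentage points.
- 21 patients (Section 13.5): 1/21 = 4.8 percentage points.

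These figures apply to any single regraded patient with no other Grade 3 or higher event. The section gives no expected frequency of such reactions, so no expected number of affected patients can be derived.

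**Step 4. Does regrading change the count of dose-limiting toxicities (DLTs)?** Section 12 requires an event of Grade 3 or higher that makes it impossible to complete radiotherapy. Section 13.5 requires an M7824-related event of Grade 3 or higher not resolved to Grade 1 or less within 28 days, or incomplete SBRT. A reaction that settles within days and leaves SBRT intact meets neither, whether it is graded 2 or 3.

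**The case against.** The best defence reads the provisions in sequence. The Grade 2\* paragraph applies after the rate has been halved, and the rate is halved only after symptoms have resolved or fallen to Grade 1. On that reading it is a residual rule for reactions that had responded and are still graded 2, while true worsening goes through the escalation clause to discontinuation. In addition, *promptly*, *rapidly*, *quickly* and *brief* carry no time limits, and the Grade 3 wording starts from a prolonged reaction and gives slow response as an example. Section 6.2.3 itself says that these reactions generally resolve within 24 hours of the end of infusion. A reaction too slow for same-day resumption need not be prolonged.

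Much of this stands. It disposes of courses C and D and leaves room for judgement at the edge of course A. It does not dispose of course B, because symptoms that return after improvement are a Grade 3 criterion in their own right. Nor does it make a reaction that fails to respond into one that responds promptly.

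Four stronger readings are tempting and are not supported:

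- A reader might infer that every reaction covered by the paragraph is Grade 3 by the table. Course C and the missing time limits rule that out.
- A reader might infer that the DLT count or the stopping boundaries in Section 13.2 are affected. Step 4 shows that Grade 3 alone is not a DLT under either definition.
- A reader might see a further contradiction in the Grade 3 or 4 instruction to restart medication. That line takes out the causative drug, which agrees with discontinuing M7824.
- A reader might make something of the asterisk on Grade 2\*. Its footnote may have been lost when the text was extracted, so nothing rests on it.

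**Conclusion.** The inconsistency is real but narrow. Where symptoms do not respond to stopping and treatment, or return on the half rate, Table 2's Grade 3 wording with its mandated discontinuation and the Grade 2 provisions for a further infusion can both apply to the same event. The case is clearest for return on the half rate. For non-response, it depends on how an investigator reads terms that have no time limit.

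The consequence is one event with two incompatible clinical instructions, plus ambiguity between Grade 2 and Grade 3 in the descriptive adverse event and AESI tables. The bounds are those of Steps 2 and 3: at most 23 further infusions for a dose-1 reaction, and 12.5 or 4.8 points per regraded patient. Neither the PFS analysis nor the DLT rule is shown to be affected. The point should be corrected because it bears on participant safety and the correction is simple. No view is taken on which rule is clinically right.

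**What to change.** Reconcile four pieces of text in Section 6.2.3: the Grade 2 row of Table 2 (including its hold clause), the Grade 3 or 4 row, the sentence mandating discontinuation, and the Grade 2\* paragraph. After the change, a reaction that does not improve, or recurs, after interruption and slowing should have one grade and one consequence wherever it is mentioned. State that the same grade is used in adverse event and AESI reporting. If the distinction is meant to rest on investigator judgement about speed of response, say so in the table and in the paragraph. The clinical lead and the supporting company decide which rule stands; none is proposed here.

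The cost is protocol wording in one table and the text after it, with no new data, visits or analyses.

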7. DEFINITION OF DISEASE PROGRESSION/RECURRENCE

Contrast-enhanced CT of neck and chest is the first choice of imaging modality. If a participant should not receive iodinated contrast medium or due to radiation protection reasons, magnetic resonance imaging (MRI) of the same area, using gadolinium enhancement according to local protocol as permitted in conjunction with unenhanced CT of the chest from the thoracic inlet to the inferior costophrenic recess should be done. The same method should be used per participant throughout the study.

A brain CT/MRI scan should be performed, if clinically indicated by development of new specific symptoms.

Baseline scans are taken within 28 days prior to treatment. Disease must be evaluable by RECIST or RECIST 1:1. All the scans performed at baseline need to be repeated at subsequent visits for tumor assessment as per Table 1 (Summary of study evaluations). In general, lesions detected at baseline need to be followed using the same imaging methodology and preferably the same imaging equipment at subsequent tumor evaluation visits.

Due to the landmark end-point of progression-free survival at 1 year, this study will utilize RECIST or RECIST 1:1.

Biopsy with histopathological confirmation of first progression is required unless contra-indicated by risk to the patient.

Disease progression will be categorized as in-field or out-of-field. For the purposes of this trial, the following definitions will be utilized:

Local progression is defined as any evidence of disease progression by RECIST or RECIST 1:1 or histologically confirmed within the re-irradiation treatment field.

Regional progression is defined as any evidence of disease progression by RECIST or RECIST 1:1 or histologically confirmed 2 cm or more outside the re-irradiation field and within the head and neck or regional lymph nodes not in reirradiation field.

Distant progression is defined as any evidence of disease involving a distant organ by RECIST or RECIST 1:1 or histologically confirmed.

Due to the known phenomenon of pseudo-progression associated with SBRT, progression should be confirmed with further evaluation which may include ultrasound, FDG-PET. Biopsy for confirmation should be considered to verify disease recurrence.

8. CRITERIA FOR SUBJECT WITHDRAWAL

8.1 Withdrawal from Trial Therapy

Participants will be withdrawn from treatment for any of the following reasons:

1. Participants meeting the definition of PD while on treatment based on RECIST or RECIST 1:1 with the exception that participant may continue past PD if the ECOG PS has remained stable, and if in the opinion of the Investigator, the participant will benefit from continued treatment.
2. In case of premature withdrawal from the study treatment for reasons other than PD, the participants will be asked to attend scheduled visits, including tumor assessment and other assessments as planned until PD and end of study or death.
3. Significant clinical deterioration (clinical progression), defined as new symptoms that are deemed by the Investigator to be clinically significant or significant worsening of existing symptoms.
4. Therapeutic failure requiring urgent additional or alternative anticancer treatment.
5. Occurrence of AEs resulting in the permanent discontinuation of the study treatment being desired or considered necessary by the Investigator and/or the participant.
6. Occurrence of pregnancy in the participant.
7. Use of a prohibited concomitant drug, as defined in Section 9.1, where the predefined consequence is withdrawal from the study treatment if considered necessary by the Investigator or the Supporting company EMD Serono.
8. Noncompliance.

8.2 Withdrawal from Study

1. A participant may withdraw from the study at any time, at his/her own request (i.e., withdrawal of consent), and without giving a reason.
2. The participant may be withdrawn by the Investigator due to participation in another clinical study.
3. The participant may be withdrawn at any time at the discretion of the Investigator for safety, behavioral, compliance, or administrative reasons.
4. The Schedule of Assessments specifies the data to be collected at study discontinuation and follow up, and any additional evaluations that need to be completed.

In case of withdrawal from the study:

1. The appropriate electronic case report forms (eCRFs) for the End-of-Treatment visit must be completed.
2. The day of withdrawal will correspond to the day of end of treatment and the assessments scheduled for the visit should be performed, if possible, with a focus on the most relevant assessments.
3. Participants will be asked to continue safety and survival follow up, which includes the collection of data on survival, patient reported outcome (PRO) questionnaires, and subsequent anticancer therapy. After completion of the Follow-up period or after the End of Treatment visit, whatever is applicable, the appropriate eCRF section for Study Termination must be completed.

If the participant is enrolled into a new study or any new therapy post-withdrawal from the study, the Safety Follow-up visit should be scheduled prior to the start of the new treatment irrespective of the 28-day safety follow up period.

8.3 Premature Discontinuation of the Trial

The whole study may be discontinued prematurely in the event of any of the following:

- New information leading to unfavorable risk-benefit judgment of the study drug, for example, due to:
 - evidence of inefficacy of the study drug,
 - occurrence of significant previously unknown adverse reactions or unexpectedly high intensity or incidence of known adverse reactions, or
 - other unfavorable safety findings.

(Note: Evidence of inefficacy may arise from this study or from other studies; unfavorable safety findings may arise from clinical or nonclinical examinations, for example, toxicology.)

- Supporting company EMD Serono's decision that continuation of the study is unjustifiable for medical or ethical reasons.

- Poor enrollment of participants making completion of the study within an acceptable time frame unlikely.
- Discontinuation of development of the Supporting company EMD Serono's study drug.

Health Authorities and Independent Ethics Committees (IECs)/Institutional Review Boards (IRBs) will be informed about the discontinuation of the study in accordance with applicable regulations.

The whole study may be terminated or suspended upon request of Health Authorities.

8.4 Definition of End of Study

If the study is not terminated for a reason given in Sections 8.1, 8.2 or 8.3, the end of the study is defined as 1 year after the last participant receives the last dose of M7824.

9. CONCOMITANT MEDICATIONS AND PROCEDURES

9.1 Permitted Medicines/Prohibited Medicines

Permitted Medicines

Any medications (other than those excluded by the clinical study protocol) that are considered necessary for the participants' welfare and will not interfere with the study drug may be given at the Investigator's discretion.

The Investigator will record all concomitant medications taken by the participant during the study, from the date of signature of informed consent, in the appropriate section of the eCRF.

Any additional concomitant therapy that becomes necessary during the study and any change to concomitant drugs must be recorded in the corresponding section of the eCRF, noting the name, dose, duration, and indication of each drug.

Blood transfusions and erythroid growth factors are permitted for hemoglobin (Hgb) \leq 7 g/dL and/or for life-threatening- bleeding.

Prohibited Medicines

As stated in the exclusion criteria, participants must not have had prior therapy with any antibody or drug targeting programmed- death 1 (anti-PD-1) or anti-PD-L1, concurrent systemic anticancer treatment, or cytokine therapy (except for erythropoietin), major surgery (excluding prior diagnostic biopsy), concurrent systemic therapy with steroids or other immunosuppressive agents, or use of any investigational drug within 28 days before the start of study treatment.

In addition, the following treatments must not be administered during the study:

- Immunotherapy, immunosuppressive drugs (ie, chemotherapy or systemic corticosteroids except for short-term treatment of allergic reactions or for the treatment of immune-related adverse events [irAEs]), or other experimental pharmaceutical products. Short-term administration of systemic steroid (ie, for allergic reactions or the management of irAEs) is allowed. Steroids with no or minimal systemic effect (topical, inhalation) are allowed. Also, hormone replacement with corticosteroids for adrenal insufficiency is allowed if the steroids are administered only for the purpose of hormonal replacement and at doses \leq 10 mg or equivalent prednisone per day.

Prophylactic use of corticosteroids for infusion-related reactions is prohibited. **However, short courses of steroids may be used at the discretion of the treating physician to prevent pain and/or swelling due to inflammation associated with SBRT, particularly transient neurogenic pain common in skull-based tumors.**

- Any vaccine therapies for the prevention of infectious disease (e.g., seasonal flu vaccine, human papilloma virus vaccine) except administration of the inactive influenza vaccine.
- If the administration of a nonpermitted concomitant drug becomes necessary during the study, the participant will be withdrawn from study treatment (the Supporting company EMD Serono may be contacted to discuss whether the study treatment must be discontinued).

Medications other than those specifically excluded in this study (see above) may be administered for the management of symptoms associated with the administration of M7824 as required. These might include analgesics, anti-nausea medications, antihistamines, diuretics, anti-anxiety medications, and medication for pain management, including narcotic agents.

Any additional concomitant therapy that becomes necessary during the study and any change to concomitant drugs must be recorded in the corresponding section of the eCRF, noting the name, dose, duration, and indication of each drug.

9.2 Permitted/Prohibited Procedures

The following nondrug therapies must not be administered during the study (and within 28 days before the start of study treatment) before the verification of PD by the IRC:

- Major surgery (excluding prior diagnostic biopsy)
- Herbal remedies with immunostimulating properties (e.g., mistletoe extract) or known to potentially interfere with major organ function (e.g., hypericin).

Any diagnostic biopsies collected for clinical reasons during the study should be documented as a concomitant procedure including the outcome of available pathological reports.

